10.2.3.8 Adherence to study treatment as self-reported by participants

10.3 Registration and Stratification

There is no randomization to this single-arm study. Eligible participants will enroll to Step 1 and then have the following required evaluations as described in section 6. The study will use stratification factors to limit enrollment to Step 1 by certain subgroups. These stratification factors include geographic location (limited to no more than 132 participants being enrolled from US-based clinic sites), HIV-1 infection (limited to no more than 200 participants being HIV-1 positive within the overall study sample) and cirrhosis status (limited to no more than 80 participants within the overall study sample having compensated cirrhosis). There are no additional restrictions regarding participants who are both HIV-co infected and have compensated cirrhosis and/or geographic distribution of those participants. Step 2 enrollment occurs following SVR evaluation and is for post SVR evaluation follow-up for selected secondary and exploratory objectives.

10.4 Sample Size and Accrual

The sample size for this single-arm study is 400 participants.

This sample size was chosen for benchmark properties listed below regarding the use of efficacy data from this study to informing the utility and feasibility of future studies of the MINMON approach, and the precision (based on CI width) about SVR efficacy outcome estimates.

Table [10.4-1](#) below describes SVR benchmarks and their properties.

The high benchmark is defined as when the lower confidence limit of the 2-sided 95% CI about the SVR estimate is strictly greater than 96%. Observing 392 or more SVR responders out of 400 participants (i.e., $\geq 98\%$ SVR responders) would meet this benchmark. Under a true SVR rate of 97%, there is only a small probability (0.15) of observing this benchmark with the study sample size of 400. However, as the true SVR rate becomes higher, the probability of observing this benchmark also increases (while holding the sample size at 400 participants). For instance, if the true SVR rate were 98.5%, then there is 0.85 probability of observing this high benchmark in the proposed study sample size of 400. If a high benchmark were observed, then a future RCT may not be needed, as the high benchmark implies that the SVR for the MINMON strategy exceeds 96%.

The low benchmark is defined as when the upper confidence limit of the 2-sided 95% CI about the SVR estimate is strictly less than 95%. Observing 371 or fewer SVR responders out of 400 participants (i.e., $\leq 92.8\%$ SVR responders) would meet this benchmark. Properties of possible scenarios are given in Table [10.4-1](#).

If neither the high nor low benchmark is met, a future RCT of the MINMON approach versus SOC may be desired, and efficacy estimates from this study could be used to inform the design and sample size of that study.

The low and high SVR benchmarks described above and in Table 10.4-1 below were chosen to represent what is currently thought to be reasonable SVR rates based on studies presented and published, including clinical trials, as well as studies reporting use of this DAA regimen outside the context of a clinical trial.

Properties of this study's sample size regarding probability of not observing either benchmark

Table [10.4-2](#) below summarizes the various probabilities that neither of the benchmarks (HIGH or LOW, as described above), are observed under a range of various true rates of SVR.

Table 10.4-1. SVR benchmarks and their properties

Benchmark	Benchmark Definition (note: CI = confidence interval)	Observed conditions for meeting benchmarks given proposed sample size of 400 participants	Hypothesized true SVR rates	Probability of observing benchmark given hypothesized true SVR rate and proposed sample size	How observing different benchmarks could inform design of a future study
HIGH	Lower confidence limit of 2-sided 95% CI about SVR estimate is strictly greater than 96%	Number of participants with SVR ≥ 392 out of 400 (or conversely, 8 or fewer SVR non-responders)	96.5%	.06	A future RCT may not be needed as this benchmark implies MINMON SVR to be greater than 96%
			97%	.15	
			98%	.59	
			98.5%	.85	
LOW	Upper confidence limit of 2-sided 95% CI about the SVR estimate is strictly lower than 95%	Observed number of participants with SVR ≤ 371 out of 400 (or conversely, 29 or more SVR non-responders)	94%	.17	A future RCT may not be desired as this benchmark implies MINMON SVR to be lower than 95%.
			93%	.45	
			92%	.74	

Table 10.4-2. Probabilities of not observing either HIGH or LOW benchmark under sample size of 400 and various true SVR rates

Hypothesized True SVR rates	Probability of not observing either benchmark as defined above (i.e., observed number of SVR responders is between 372 – 391, inclusive, out of 400 participants)
90%	.023
91%	.092
92%	.264
93%	.550
94%	.829
95%	.968
96%	.978
97%	.849
98%	.407
99%	.021

Table 10.4-3 below summarizes the precision about the primary efficacy outcome of SVR (as measured by the width of the 95% CI about the SVR estimate), and location of 95% CI limits, based on various observed SVR rates and 400 individuals. The 95% confidence intervals were calculated with the binomial distribution according to the method of Wilson (Score based intervals).

Table 10.4-3. Summary of a range of observed SVR rates and their impact on the precision of the 95% CI about the observed/estimated SVR rate

Observed SVR rate among n=400	SVR 95% CI lower confidence limit	SVR 95% CI upper confidence limit	Precision of SVR estimate (95% CI width in percentages points)
90%	86.7%	92.6%	5.9
91%	87.8%	93.4%	5.6
92%	88.9%	94.3%	5.4
93%	90.1%	95.1%	5.0
94%	91.2%	95.9%	4.7
95%	92.4%	96.7%	4.3
96%	93.6%	97.5%	3.9
97%	94.8%	98.3%	3.4
98%	96.1%	99.0%	2.9
99%	97.5%	99.6%	2.2

The sample size calculation has not been adjusted for losses to study follow-up as the definition of the primary efficacy outcome includes imputing missing evaluations as SVR non-responders. The impact of missingness contributing to the (lowering of the) SVR response rate will be addressed by both enumerating what led to non-SVR responder classification such as the following: missing HCV RNA values for SVR evaluation, HCV

RNA values observed >the assay LLOQ, early stopping of study treatment (e.g., for intolerance, etc.).

Assuming uniform accrual of 25 participants per month, total accrual to the study would be completed in 16 months. If initial accrual is assumed to be slower, at rates of 10 participants per month for the first 6 months, 15 participants per month for the next 6 months, and 20 participants per month for the remaining time, the total accrual time would be about 24 months.

10.5 Data and Safety Monitoring

10.5.1 Interim Monitoring Guidelines

This study will be formally monitored at least annually by an ACTG-appointed SMC (via the standing committee for the Hepatitis TSG). The first interim review will occur no more than one year after the enrollment of the first study participant or 6 months after 25% of the study sample (100 participants) have completed 12 weeks on study, whichever occurs earlier.

A planned interim review for efficacy will be performed when SVR outcomes are available for approximately 100 participants, but could occur earlier (under case of a faster than anticipated accrual rate). The team wishes that an interim look at efficacy occur while the study is still accruing, so that if SVR rate is unacceptably low (i.e., futility), that there is still an opportunity to intervene before accrual to the study is completed.

For instance, assuming uniform accrual of 25 participants per month and SVR evaluation happening 24 weeks following study entry, the planned interim review for efficacy would occur around month 12 since study accrual commenced, with approximately 300 participants accrued, 100 participants with SVR outcome available, and 100 participants remaining to be accrued. Assuming the slower but increasing accrual rate over time and same timing of SVR evaluation, the planned interim review for efficacy would occur approximately 17 months following study opening, with approximately 265 participants accrued, 105 participants with SVR outcome, and 135 participants remaining to be accrued.

Consideration would be given to closer monitoring or stopping the study if there is early and strong evidence to exclude the SVR rate from being 95% or higher (i.e., upper confidence bound on a 1-sided 99.9% CI is lower than 95%). With 100 participants, this boundary would be met if the observed SVR rate were 86% or lower (which corresponds to 14 or more SVR non-responders out of 100). For additional information, SVR estimates will be provided separately for subgroups defined by geographical location stratification factor (ie, US versus non-US).

However, if the SMC sees early benefit of the MINMON intervention, the team intends the study to proceed with full accrual and follow-up in order to confirm early evidence, and gain precision on the efficacy outcome estimate and other

outcomes. At interim reviews, SVR will be calculated only among those with potential to contribute to SVR (by having at least 22 weeks elapsed since study entry). Imputation of missing SVR evaluation as non-SVR response will only occur for participants for whom more than 76 weeks since study enrollment has elapsed. In other words, early study discontinuations prior to week 22 will not be counted in SVR estimation at interim review, as these could bias the estimation of SVR towards futility. Instead, these early study discontinuations prior to week 22 (before available for SVR evaluation), and others missing SVR evaluation, will contribute to the interim monitoring trigger below.

If the analysis sample for the initial planned review for efficacy as outlined above includes fewer than 40% participants from non-US clinical research sites, then a second planned review of efficacy will be triggered when SVR outcomes are available on approximately 230 participants (with the upper limit of US participants of 132, this estimates at least 40% non-US representation in the second efficacy look interim analysis sample). The same analysis plan and monitoring bounds as defined in the first look above would be applied to this second look at SVR.

An unplanned interim review will be triggered if, at any time, more than 20 persons are not evaluable for the SVR outcome before study discontinuation or 76 weeks following study enrollment. Another trigger for an unplanned interim review is if, at any time, the number of participants experiencing an SAE exceeds 5% of the interim analysis dataset, and the absolute number of participants with SAEs at least 10 (as 5% was the observed upper bound of the 95% CI on number of participants with any SAE from the ASTRAL-5 trial).

Any/all SMC reviews will include administrative/trial conduct data as well as safety data according to the safety-related outcomes enumerated above.

The following routine monitoring reports are distributed to core team and are detailed in the study monitoring plan (SMP): screening, accrual, data delinquency, study status, data and sample completeness, with attention to evaluation and timing of SVR outcome. The routine safety monitoring report is distributed to the DAIDS Clinical Representative and a subset of the core team (to include the study chairs) every 3 months.

Further details about monitoring of this study are available in the SMP.

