6.2.4 Post-Entry Evaluations

Given the design of the MINMON strategy, there will be no on-treatment or EOT evaluations. See section 6.3.22 for post-entry site contact with participants via remote mechanism.

Post-Treatment Evaluations

Step 1: Following treatment completion at week 12, participants will undergo evaluations as outlined in the SOE 6.1-1.

NOTE: If the participant comes in for the week 24 visit during the -14 days window (i.e., week 22), then the week 22 remote call is not needed.

Week 24/SVR Evaluation Visit

The week 24 visit (visit window: week 22-28) is ideally the visit where SVR should be assessed for all participants, and subsequently they will be registered to Step 2. However, if a participant misses the visit window (>week 28), the week 24 visit will be considered a missed visit and he/she will need to be scheduled for an SVR visit prior to being registered to Step 2 of the study. The SVR visit can

take place at any time point after week 28 and up to week 72 and is mandatory for the participant to be registered to Step 2.

NOTE: Participants will be reminded of the week 24/SVR visit during the remote contact (at weeks 4 and 22), and participants only need to complete either the week 24 OR the SVR evaluation visit; they will not be required to complete both. If a participant completes week 24, his/her next visit will be at week 48 on Step 2. If a participant misses the week 24 visit and returns to the clinic for the SVR visit either at week 48 or 72, then only the SVR evaluations will be performed at that visit time point. Evaluations for weeks 48 or 72 will be performed at the next scheduled study visit. However, if a participant completes their SVR visit at week 72, this visit will be the participants' last study visit and they will not enter Step 2.

Step 2 Registration

Following completion of the SVR evaluation on Step 1 (Week 24 OR SVR visit), participants will be registered to Step 2 on that same day. Participants will undergo evaluations as outlined in the SOE 6.1-2, within the ±28-days visit window, as appropriate for the visit.

NOTE: Participants who register into Step 2 within the week 48 visit window will complete the week 48 and 72 visits. If a participant registers into Step 2 after the week 48 visit window, site staff should have the participant return to the clinic to complete week 72 (final study visit).

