10.2 Outcome Measures

10.2.1 Primary Outcome Measures

- 10.2.1.1 Efficacy: Sustained virologic response defined as <LLOQ of HCV RNA in plasma from the earliest sample drawn at least 22 weeks following study entry. Missing results will be treated as SVR non-responders.
- 10.2.1.2 Safety: SAEs as defined by International Council for Harmonization (ICH) guidelines occurring from study entry until 24 weeks following study entry.

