4.1 Primary Outcome Measures

4.1.1 Primary Efficacy Outcome Measure

Measure Title: *Percentage of Participants with Sustained Virologic Response 12 (SVR12)*

Measure Description: *SVR12 was defined as plasma HCV RNA less than the lower limit of quantification (LLOQ) from the earliest sample drawn at least 22 weeks following study treatment initiation (i.e. at a visit scheduled at least 10 weeks after scheduled end of study treatment). Participants without any HCV RNA result at least 22 weeks after treatment initiation will be considered as having HCV RNA greater than the LLOQ.*

A two-sided 95%, confidence interval was calculated for this percentage using the Wilson (score) method.

Time Frame: *At least 22 weeks and up to 76 weeks from treatment initiation.*

Population Description: *Participants who enrolled and received first dose of study medication.*

Associated study objective: *“To estimate SVR (defined as HCV RNA < lower limit of quantification [LLOQ] at least 10 weeks after the end of treatment [EOT] [which is at least 22 weeks from the study entry visit date]).”*

Details: Due to the definition of SVR outcome measure, missing HCV RNA results will lower the overall percentage of participants with SVR. Therefore, various reasons for non-SVR (e.g., discontinued treatment early due to various reasons including intolerance, observed HCV RNA \geq LLOQ, missing evaluation for SVR (and reasons as known), and the number of participants meeting each reason for non-SVR, will be presented in order to interpret the overall SVR sample estimate.

For interim analyses: Interim analysis is planned when SVR outcomes are available for approximately 100 participants. At interim reviews, SVR will be calculated only among those with potential to contribute to SVR (by having at least 22 weeks elapsed since study entry). Imputation of missing SVR evaluation as non-SVR response will only occur for participants for whom more than 76 weeks since study enrollment has elapsed. In other words, early study discontinuations prior to week 22 will not be counted in SVR estimation at interim review, as these could bias the estimation of SVR towards futility. Instead, these early study discontinuations prior to week 22 (before available for SVR evaluation), and others missing SVR evaluation, will contribute to the interim monitoring

trigger. For more details, refer to Overview of Formal Interim Monitoring of section 3.5 above.

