5.1.3 Analysis Sets

Enrolled participants who do not start study medication will be excluded from all analyses. Note that per protocol instructions, the first dose of study medication is to be observed in the study clinic during the entry evaluation visit.

Full analysis sample (= Efficacy analysis sample at final analysis): Participants who started study medication. For the efficacy analysis sample for interim reviews, refer to section: 4.1.1 Primary Efficacy Outcome Measure. At interim analyses, the efficacy analysis sample will differ from the full analysis sample as follows: participants missing HCV RNAs for SVR evaluation will not be counted as SVR non-responders unless they enrolled more than 76 weeks prior to dataset finalization. Thus, the efficacy analysis sample at interim reviews will be based on observed HCV RNAs in the SVR evaluation window plus participants who both left the study without a result for SVR evaluation and who enrolled more than 76 weeks ago (and thus can no longer be evaluated for SVR on study).

Safety analysis sample: Participants who started study medication and who were evaluated for AEs for the time period after first dose of study treatment through up to 24 week later. This criterion will be met for any participant having an unscheduled visit prior to week24/SVR evaluation, or any participant having a week 24 or SVR evaluation visit. At interim analysis, due to no planned study clinic visits prior to study week 24, this analysis sample include all participants who started treatment, and only exclude those who were both known lost to all follow-up and without any follow-up for AEs. This sample will be split into subgroups defined by those having week 24/SVR evaluation visit versus not.

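### Should the interim futility bound, and the trigger of more than 20 non-evaluable participants, count people without an SVR result sooner than 76 weeks?

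*Protocol*

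**What the plan says.** Protocol 10.2.1 defines the primary efficacy outcome with the rule "Missing results will be treated as SVR non-responders". Interim reviews work differently. SAP 4.1.1 states "At interim reviews, SVR will be calculated only among those with potential to contribute to SVR", meaning at least 22 weeks since entry, and Protocol 10.5.1 adds "Imputation of missing SVR evaluation as non-SVR response will only occur for participants for whom more than 76 weeks since study enrollment has elapsed". SAP 5.1.3 builds the interim efficacy sample to match: observed HCV RNA results in the SVR window, "plus participants who both left the study without a result for SVR evaluation and who enrolled more than 76 weeks ago".

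Protocol 10.5.1 gives the reason. Early discontinuations are left out of the interim SVR "as these could bias the estimation of SVR towards futility". They are sent to a second channel instead: these people, "and others missing SVR evaluation, will contribute to the interim monitoring trigger below". That trigger calls an unplanned review if, at any time, "more than 20 persons are not evaluable for the SVR outcome before study discontinuation or 76 weeks following study enrollment".

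The interim bound itself is advisory. Closer monitoring or stopping would be considered if a one-sided 99.9% upper limit for SVR fell below 95%, given as 14 or more non-responders in 100. Under Protocol 6.2.4, a participant who misses the week 22–28 window is not lost: the SVR visit may "take place at any time point after week 28 and up to week 72".

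**The concern.** The interim and final quantities differ. A participant who has permanently left before testing can only be a non-responder in the final analysis, yet is absent from the interim SVR and its bound. The stated reason is sound for people who may still be tested. It is less obviously sound for a known leaver whose contemporaries have already had their SVR visit.

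The trigger might not fill the gap. Its wording fixes non-evaluability at study discontinuation or at 76 weeks. Read literally, a participant who simply stops responding does not count until 76 weeks. That is later than the first efficacy look and, under uniform accrual, later than the end of accrual at month 16.

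The look is timed to fall during accrual so that the team can act if SVR is unacceptably low. Non-return is a risk the protocol itself raises (section 2.2). If SVR on the primary definition were low because people did not come back, neither channel might show it in time.

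**Working it through.** **1. The plan's own boundary.** Inputs (Protocol 10.5.1): one-sided 99.9% limit, 95% reference, n = 100. The exact binomial upper limit is 94.59% at 86/100 and 95.21% at 87/100, so 14 non-responders meet the bound and 13 do not. The stated figure is reproduced.

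**2. Who is past 76 weeks at the first look.** One month is 365.25/(12×7) = 4.348 weeks, so 76 weeks is 76/4.348 = 17.48 months. Month 12 is week 52.2 and month 17 is week 73.9: nobody qualifies at either. At the slower accrual rates, 150 are enrolled by month 12 and 265 by month 12 + 115/20 = 17.75. About 10 × (17.75 − 17.48) = 2.7 people are then past 76 weeks. The first-look bound therefore uses observed results, apart from at most about three people.

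**3. What the bound cannot see.** Take 97 of 100 observed cured, plus 12 known leavers. As written, the rate is 97.0% with upper limit 99.8%, not crossed. With leavers counted it is 97/112 = 86.6% with upper limit 94.6%, crossed.

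Now assume 98% SVR if tested and 10% or 12% permanent loss. The documents give no permanent-loss rate; the figure of about 20% in Protocol 2.2 concerns US patients who do not return in a timely manner.

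- SVR on the primary definition: 0.98 × 0.90 = 88.2%; 0.98 × 0.88 = 86.2%.
- Observed-only bound: P(X ≤ 86 | 100, 0.98) = 1.4 × 10⁻⁸.
- Final low benchmark: P(X ≤ 371 | 400) = 0.999 or higher. At 5% loss (93.1%) it is 0.42.

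The contrast between 10⁻⁸ and 0.999 is not like for like. The second figure uses 400 participants and a two-sided 95% interval; the first uses 100 and a 99.9% limit.

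**4. The fair comparison: the same bound with known leavers counted.** Failure probability is q + (1 − q) × 0.02, that is 0.118 at q = 10% and 0.138 at q = 12%. One sample size is 100/0.9 = 111. The other is everyone at least 28 weeks (6.44 months) from entry at month 12: 25 × (12 − 6.44) = 139. The exact boundaries are 15 of 111 and 17 of 139.

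| Probability of crossing | 10% loss | 12% loss |
|---|---|---|
| n = 111, all losses known | 0.33 | 0.57 |
| n = 139, all losses known | 0.48 | 0.74 |

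If only half the losses are known, these fall to roughly 0.02–0.07. At 5% loss, all known, they are 0.01–0.02.

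**5. The existing trigger on its literal wording.** Assume formal discontinuations spread evenly over the first 22 weeks (5.06 months), with silent no-shows counted only at 76 weeks. At month 12 with uniform accrual and 10% loss, all formal, the expected count is 0.10 × [25 × (12 − 5.06) + ½ × 25 × 5.06] = 23.7. Probability that the count exceeds 20:

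| Share of losses formal | Month 12, 10% loss | Month 12, 12% loss | Month 17, 10% loss | Month 17, 12% loss |
|---|---|---|---|---|
| 25% | <0.001 | <0.001 | <0.001 | <0.001 |
| 50% | 0.01 | 0.05 | 0.001 | 0.01 |
| 75% | 0.24 | 0.56 | 0.07 | 0.26 |
| 100% | 0.75 | 0.95 | 0.44 | 0.77 |

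Where losses are known, the trigger is at least comparable with the modified bound: better at month 12 and similar at month 17. Where losses are silent, both are weak.

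**6. Counting a missed week 22–28 window towards the trigger.** With 25–50% of losses formal, the month-12 firing probability rises to 0.14–0.33 at 10% loss and 0.40–0.67 at 12%. There is a price. Suppose 15% miss the window but 80% of them are tested later, so 3% are lost permanently. Final SVR is 0.98 × 0.97 = 95.1%, yet P(more than 20 of 139 miss the window) = 0.52. An SVR display with every missing result as failure would read 0.98 × 0.85 = 83.3% in the same situation.

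**The case for a change.** The best case for a change is narrow. The plan's reason for excluding early leavers does not strictly apply to known permanent leavers in a cohort already past week 28, because counting them there would not run ahead of their contemporaries' results. The two sentences on the trigger also sit awkwardly together. One says that others without an SVR evaluation contribute, without saying when; the other implies 76 weeks. If loss were moderate and mostly silent, the literal trigger would rarely fire at the first look, and the listed review items include no SVR estimate on the primary scale. An extra display in the committee's report would cost little.

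All of that stands as description. It does not show that the plan misleads its committee. Protocol 7.4 and SAP 3.5 put study discontinuation, data completeness and evaluability for the primary efficacy outcome before the committee. SAP 5.1.3 splits the safety sample by whether the week 24/SVR visit took place. The core team's routine reports cover completeness and timing of the SVR evaluation, and a review can be called on any concern. A committee holding the observed SVR and the evaluability counts can work out the missing-as-failure figure for itself.

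The extra display would alter no stopping rule, and a bound limited to known leavers would not reach the silent losses that make up the gap.

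**Conclusion.** No change is needed. The observation is accurate: at the first efficacy look the bound is in effect an observed-results bound, and on a literal reading silent no-shows do not yet count towards the trigger. But this is a disclosed trade-off, stated consistently in Protocol 10.5.1 and SAP 4.1.1 and 5.1.3. Virologic failure is monitored by the bound, and loss by the trigger and the evaluability review. The bound is advisory, and the final estimate still counts every missing result as non-response.

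The alternatives gain little. Counting known leavers in the bound gives a crossing probability of 0.33–0.74 in the very setting where the trigger already fires with probability 0.75–0.95 (month 12) or 0.44–0.77 (month 17), and roughly 0.02–0.07 when half the losses are unknown. Counting missed windows adds sensitivity, but brings a 0.52 chance of an unplanned review in a benign late-return case.

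What remains is a small gap in wording: when a no-show who has not discontinued starts to count. Protocol 10.5.1 refers to the study monitoring plan for further detail. That plan is not among the documents and may already settle the rule; if it does not, the statisticians can fix it there.

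These figures rest on assumed values of 98% SVR if tested, 10–12% permanent loss, and stated shares of formal discontinuation. The exposed region is moderate, mostly silent loss; at 5% loss even the modified bound would almost never be crossed.

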6.3.22 Remote Contact with Participants Outside of Planned Clinic Visits

When contacting participants remotely, sites will have the flexibility to make adjustments to the mode of contact utilized at their discretion and at the participant's convenience – the only mode that will not be allowed is to schedule clinic visits in place of the remote contact. Sites will also be able to use different modes to contact different participants. Additionally, how the participant was contacted (i.e., mode of contact) will be collected on the eCRF.

Data that will be captured from the participant during the week 4 remote contact is whether the participant is taking study medication (i.e., adherence), in the prior 4 weeks. All participants will receive an individually tailored message, based on their adherence, which will be read or written to them in order to promote and/or encourage adherence through the end of treatment. The message will highlight the benefit of treatment for HCV and the importance of adherence and will be tailored to each participant's response as to how well he/she is adhering to the HCV treatment regimen. Additionally, at both weeks 4 and 22, locator information will be updated (if anything has changed) and participants will be reminded to return for their SVR evaluation visit. Sites will be allowed to contact and collect participant's responses on adherence and to update his/her locator information using any of the options listed above, namely phone call, text message, email, or social media (e.g., WhatsApp, Facebook Messenger, Twitter, etc.; for a complete list, please refer to the MOPS). If the participant comes in for the week 24 visit prior to the completion of the week 22 remote call, or if the participant has completed the discontinuation visit, then the week 22 remote call is not needed.

The remote contact is not designed to assess concomitant medications or AEs. At the end of each remote contact, participants will be reminded that the information that they shared will not be communicated to the study team and that if they have concerns about symptoms or study questions they should contact the site via the telephone number provided by the site. This information should be reported in a medical record then reviewed and entered into an eCRF at the week 24/SVR evaluation visit.

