8.0 CLINICAL MANAGEMENT ISSUES

8.1 Toxicity

Criteria for participant management, dose interruptions, dose adjustments and discontinuation, or changes in treatment will be described only for toxicities attributable to study drugs (SOF/VEL). The grading system for drug toxicities is located in the DAIDS AE Grading Table (see section 7.2).

NOTE: The team must be notified via e-mail within 72 hours regarding toxicities that result in a change in study regimen ([contact]).

It is possible that some participants will experience transient or prolonged AEs during the study. However, it is important to note that, in this trial, there are no scheduled on-treatment visits and hence, participants must call the site and schedule unplanned study visits in order for AEs to be identified. AE-related unplanned study visits will be handled as listed below. However, at week 24, information on any AEs participants may have experienced during the prior 24 weeks, particularly while on study medication, will be collected.

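### The SAE review trigger sets known SAEs against a denominator that, on the SAP's reading, includes many participants not yet asked about adverse events, so it is diluted and fires late

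*Protocol*

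**What the plan says.** Protocol 10.5.1, repeated in SAP 3.5, triggers an unplanned review by the Study Monitoring Committee (SMC) whenever "the number of participants experiencing an SAE exceeds 5% of the interim analysis dataset". A second condition must hold as well: "the absolute number of participants with SAEs at least 10". The rule applies throughout the study, not only at scheduled looks. The 5% is justified by an earlier trial: "as 5% was the observed upper bound of the 95% CI on number of participants with any SAE from the ASTRAL-5 trial".

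Neither section says which dataset is meant. SAP 5.1.3 gives the only interim safety sample: "this analysis sample include all participants who started treatment, and only exclude those who were both known lost to all follow-up". Exclusion also requires that no adverse event (AE) information was obtained from the participant. The SAP adds: "This sample will be split into subgroups defined by those having week 24/SVR evaluation visit versus not". The trigger is not linked to that split.

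AE information before week 24 depends on the participant. Protocol 8.1 says that "participants must call the site and schedule unplanned study visits in order for AEs to be identified". Protocol 6.3.22 says of the scheduled calls and messages: "The remote contact is not designed to assess concomitant medications or AEs". Protocol 7.2 and 8.1 place the systematic AE enquiry at the week 24/SVR visit.

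For the planned efficacy look under uniform accrual, Protocol 10.5.1 expects "approximately 300 participants accrued, 100 participants with SVR outcome available".

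**The concern.** The numerator can contain only SAEs that someone has reported. On the SAP 5.1.3 reading, the denominator also counts people from whom no one has yet sought AE information. The 5% comes from the proportion of participants with any SAE in another trial, so the two sides of the comparison do not match. The result depends on how far accrual runs ahead of week 24 visits as well as on the SAE risk.

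The same protocol section avoids this for efficacy: interim SVR is calculated only among participants at least 22 weeks from entry. The SAE trigger has no such restriction.

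At stake is timing. This is the only numerical study-level SAE threshold in a strategy with no scheduled on-treatment visits. A late trigger means that more participants start treatment before the review is called.

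**Working it through.** **The plan's own counts (Protocol 10.5.1).** Uniform accrual at 25 per month gives 25 × 12 = 300 at month 12, as stated. Week 24 is 24 × 7 / 30.4375 = 5.52 months, so by visit date 25 × (12 − 5.52) = 162 would have been seen, not 100. The stated 100 needs 8 months from entry to available result: 25 × (12 − 8) = 100. The slower scenario's 105 at month 17 implies the same 8 months (10 × 6 + 15 × 3 = 105 enrolled by month 9). Its accrued count comes to 60 + 90 + 100 = 250 at month 17, against about 265 stated; the stated figure is used below. Both clocks, 24 weeks and 8 months, are carried forward.

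**Threshold.** With N in the denominator, the rule needs k = max(10, floor(0.05N) + 1) participants with an SAE. N = 300 gives 16, N = 265 gives 14. For N = 100, 105 or 162 the floor of 10 governs.

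**Single look, true risk 10%, no SAE known before assessment.** P = P(Bin(assessed, 0.10) ≥ k). The 10% is a scenario, not a figure from the documents.

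| Treated | Assessed | k as written | P as written | k matched | P matched |
|---|---|---|---|---|---|
| 300 | 100 | 16 | 0.04 | 10 | 0.55 |
| 265 | 105 | 14 | 0.16 | 10 | 0.61 |
| 300 | 162 | 16 | 0.56 | 10 | 0.97 |

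In the first row, 16 of 100 assessed is an observed rate of 16%.

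**Monitoring at any time.** Simulation of 400 entrants at 25 per month, with SAE onset uniform over weeks 0-24. A share q of SAEs is known at onset and the rest at assessment (24 weeks or 8 months after entry). All participants are assumed to be assessed. The documents give no value for q. The proposed rule fires if either denominator exceeds 5%, with at least 10 SAE participants overall.

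| True risk | q | Fires before accrual ends, as written | With matched criterion added |
|---|---|---|---|
| 8% | 0, both clocks | 17-63% | 95-99% |
| 8% | 0.25, 8 months | 40% | 97% |
| 5% | varied | 0-22% | 51-69% |
| 3% | varied | 0-1% | 8-13% |

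At 8% and q = 0, firing by month 12 is 1% against 29% (8 months) or 31% against 85% (24 weeks).

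At 10% and q = 0, the written rule fires before accrual ends in about 50-55% of runs (8 months) or 91-94% (24 weeks). Under slower accrual these become 84% and 98%. At 10% with the 8-month clock and uniform accrual, the written rule has fired by month 12 in 36% of runs at q = 0.25, 70% at q = 0.5 and 98% at q = 1.

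At exactly 5%, by end of follow-up, the written rule fires in about 42-48% and the proposed rule in about 70-78%.

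**The case against.** A reader might infer that the trigger rarely fires during accrual even at twice the ceiling. The documents do not support that. The rule applies at any time, and at a true 10% it fires before accrual ends in half or more of runs even if no SAE is known early. Late is the right word.

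A reader might also infer that most participants are unassessed at the planned look. That treats available SVR outcomes as AE assessments. By visit date, 300 − 162 = 138 of 300 (46%) are unassessed at month 12; the share is above half only until about month 11.

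Further points on the other side:

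- **The denominator is an inference.** If the dataset means the interim efficacy sample, the floor of 10 governs at 100 participants and the probability is already 0.55. A Study Monitoring Plan that is not among these documents may settle it. This stands, and is itself a reason to define the term.
- **The planned look is already an SMC review.** It includes safety data, and the SAP's split would show the assessed group. This stands, so the trigger matters most between scheduled reviews.
- **Other safeguards exist.** SAEs are entered in the expedited reporting system once known, summaries are prepared quarterly, and any concern can prompt a review. These limit the harm, but they rest on the same participant-initiated reporting before week 24, and none sets a numerical SAE threshold.
- **Restricting to attenders has a selection problem.** Deaths and losses after an SAE would drop out. This stands and shapes the fix.
- **A single-look false-alarm rate understates the cost.** At 100 assessed and a true 5% the matched rule fires with probability 0.03, but the rule is applied continuously. This stands; the cumulative figures are the ones to disclose.

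**Conclusion.** The point holds as one of definition and delay. The trigger's dataset is undefined. On the only interim safety sample in the documents, numerator and denominator come from different stages of follow-up. The loss is large at the planned look if assessment runs on the 8-month clock (0.04 against 0.55 at a true 10%) and smaller but still material on the visit clock (0.56 against 0.97). Over accrual at a true 8%, it is 17-63% against 95-99%.

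These figures assume that no SAE is known before assessment. The loss largely disappears if nearly all are known at onset. They also rest on the SAP 5.1.3 reading and on risks of 8% and 10% chosen as scenarios. The 5% ceiling cannot be checked, because the documents give no SAE count for the trial it came from.

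**What to change.** In Protocol 10.5.1, SAP 3.5 and the monitoring plan, define the dataset and apply the 5% to two groups:

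1. All treated participants, as in SAP 5.1.3.
2. Participants who have had the week 24/SVR visit, or whose week 24 window has closed with AE information available. This includes deaths and participants lost after a reported SAE. Numerator and denominator come from the same people.

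Keep the floor of 10 SAE participants overall, and call the unplanned SMC review if either proportion exceeds 5%. State the rule's operating characteristics under continuous monitoring.

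The change needs a short amendment and no new data, since the SAP already makes most of the split. The cost is more reviews. By end of accrual the added criterion fires in about 8-13% of runs at a true 3% and 51-69% at exactly 5%, against about 0-1% and 0-22% as written. The written figure at 5% is higher if every SAE is known at onset (42-43% under slower accrual). Part of the increase is earlier timing: by end of follow-up at 5% the comparison is about 70-78% against 42-48%. The consequence is a committee review, not a stop, at a rate equal to the ceiling the protocol chose.
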